A Pilot Dose-Response Biomarker Study of Brexpiprazole Treatment in PTSD
(Terminated)

NCT02934932

Document Date: February 3, 2017

1. Title: A Pilot Dose-Response Biomarker Study of Brexpiprazole Treatment in PTSD

2. Purpose of the Study: To determine if brexpiprazole treatment will be associated with a dose-dependent reduction in resting pupil diameter as a reflection of locus coeruleus (LC) norepinephrine (NE) neuron target engagement in a group of subjects with PTSD. To determine if brexpiprazole therapy will also be associated with a dose-dependent decrease in the clinician administered PTSD scale (CAPS-5) scores. To determine if the pre-post treatment change in resting pupil diameter will be statistically significantly correlated with the pre-post change in CAPS-5 score.

3. Primary Objectives:

Specific Aim 1: Evaluate the effects of two doses of brexpiprazole on locus coeruleus (LC) norepinephrine (NE) neuron activity.

Specific Aim 2: Determine the effect of brexpiprazole therapy on PTSD symptom severity.

Specific Aim 3: 1) Evaluate whether depression severity improves with treatment and assess how this relates to PTSD response; 2) Specifically evaluate the degree to which treatment improves nightmares; 3) Evaluate the effects of treatment on sleep disturbance.

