4. Background & Significance: Post-traumatic stress disorder (PTSD) adversely affects an individual's emotional and physical well-being, quality of life, and functional abilities, and increases suicide risk (Finley et al., 2015). The lifetime prevalence of PTSD varies substantially depending on the population (military, police, general adult population), but lifetime estimates are reported to be at around 10% (7.8% in the United States, 9.2% in Canada and 12.2% in Australia). Hyper-arousal is extremely common in individuals with PTSD and is considered a hallmark of the disorder. Locus coeruleus (LC) norepinephrine (NE) neuron dysregulation is believed to contribute to dysfunctional arousal in patients with PTSD and is a neurobiological target of interest. For instance, LC NE reuptake transporter labeling using PET scans correspond with anxious-arousal symptoms such as hypervigilance in subjects with PTSD. Brexpiprazole is of interest as a treatment for reducing dysfunctional arousal in PTSD patients based on its receptor binding profile which includes 5-HT_{1A} receptor activation and 5-HT₂ receptor antagonism. The brainstem circuit which involves 5-HT neuron regulation of LC NE neuron activity is complex and includes 1) activation of 5-HT_{1A} receptors that decrease 5-HT neuron activity mediated 5-HT release and 2) 5-HT₂ receptor antagonism on GABAergic projection neurons to the LC, which 3) renders an increase in α_2 -autoreceptor mediated regulation of NE neurons (Blier and Szabo, 2005). However, the effects of this agent on patients with PTSD have not been evaluated. A factor confounding pursuing a study of the effects of brexpiprazole in patients with PTSD is preclinical data which suggest that there might be an increase in LC function with brexpiprazole at least with some doses suggesting that this agent may have important dose-dependent effects on LC function which, in turn, suggests that the therapeutic effects in patients with PTSD might be highly dose-dependent. However, whether there is a dose-dependence to the effects on LC function in humans has yet to be determined. It is critical that the uncertainty as to the appropriate dosage be addressed before carrying out sizable studies of the effects of brexpiprazole on patients with PTSD to prevent such studies from being futile. In order to address this uncertainty we propose to carry out a biomarker study to establish the effects of brexpiprazole on LC NE activity as a function of dose where pupillometry will be employed as an indicator of LC NE activity.

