
Pupillometry is a well-established, non-invasive, inexpensive indicator of LC NE activity. LC NE neuron activity increases pupil size through activation of Edinger-Westphal neurons which project to sympathetic ganglia controlling pupil diameter. Recent work has validated pupillometry as a measure of LC NE activity by simultaneously obtaining EEG, fMRI, and pupillometric data. Furthermore, the utility of pupillometry as a

biomarker of PTSD is suggested by a recent study which found increased pupil responses to threatening pictures in subjects with PTSD compared to those without PTSD. Thus, we propose to carry out a study employing pupillometry as a means of establishing the dose-response function of brexpiprazole on a key target of PTSD therapy as a means of addressing the uncertainty in dose generated by preclinical work indicating that, at least at some dosages, brexpiprazole may increase LC NE activity. We will also collect preliminary data on the dose-response effects of brexpiprazole on the clinical symptomatology of PTSD. Overall, this study is intended to provide a basis for determining the potential of brexpiprazole to be an effective therapy for PTSD. If brexpiprazole appears to be a promising therapy for this condition, our study will also serve as a basis for indicating how best to carry out clinical trials.

The broad impetus for this effort is the urgent need to develop improved therapeutics for PTSD. Treatments for this condition are extremely limited and none have demonstrated robust efficacy. It is hoped that the proposed study will serve as a key step towards evaluating whether brexpiprazole could be a much needed efficacious treatment for the many patients suffering from PTSD.

5. Design & Procedures

5.1 Subject recruitment: Participants will be recruited by running approved study specific advertisements in local newspapers and posting study flyers in the local area. We plan to consent up to 100 subjects to recruit 36 study qualifiers. Single site, double-blind, within-subjects, cross-over, dose-response study of brexpiprazole in subjects with PTSD to evaluate the effects of brexpiprazole dose on LC NE neuron activity using pupillometry and CAPS-5 ratings.

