Subjects will be screened and will undergo pupil measures with rating scales on Day 1. Subject must be free of all psychotropic medications for one week before Day 1 assessment, except that prior fluoxetine treatment will require 4 weeks of abstinence, and MAOIs will require 2 weeks of abstinence. They will be randomized to study drug and issued six weeks of study medication on Day 1 to take home. A phone call will then occur for safety assessment and medication adherence at every week. They will present back to the study site on Day 42 and undergo pupil measures with rating scales. They will then undergo a one week washout period. On Day 49 they will then be given another study drug to take home with rating scales and pupil measures obtained that day. A phone call will then occur for safety assessment and medication adherence at every week. They will present back to the study site on Day 91 and undergo pupil measures with rating scales. They will then undergo a one week washout period. On Day 98 they will then be given another study drug to take home with rating scales and pupil measures obtained that day. A phone call will then occur for safety assessment and medication adherence at every week. They will present back to the study site on Day 140 and undergo pupil measures with rating scales. No more study medication will be provide on Day 140 and a final visit will be scheduled for on Day 147, one week later, for and end of study interview with labs and physical exam. At each visit, other than the final visit, subjects will complete the CAPS-5, LEC-5, MADRS, Insomnia Severity Index, Columbia Suicide Severity Rating Scale, and Clinician Assessment for Adverse Effects.

5.3 Pupilometry Procedure. We will employ Tobii Tracker Eyeglasses 2 (Stockholm, Sweden) fully mobile Eye-tracking Glasses, a non-invasive system designed to be used like a common pair of glasses (weight 75 g) in a wide range of environments, both indoors and outdoors. Pupil diameter will be recorded continuously from the each eye at a sampling rate of 50 - 100 Hz via glasses on the subject's face in a darkened room.

Primary Hypothesis: Brexpiprazole treatment will be associated with dose-dependent reduction in resting pupil diameter as a reflection of LC NE neuron target engagement in a group of subjects with PTSD.

Secondary Hypothesis: Brexpiprazole therapy will be associated with a dose-dependent decrease in CAPS-5 scores

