Tertiary Hypothesis: The pre-post treatment change in resting pupil diameter will be statistically significantly correlated with the pre-post change in CAPS-5 score.

Version: 2/3/2017

5.4 Sample Size Justification and Power Analysis: We chose an effect size of 0.3 as 6/8 prior trials of the effects of atypical antipsychotic medications on PTSD using the CAPS-5 had effect sizes larger than this and we felt that an effect of this size or larger would be clinically relevant (Liu et al., 2014). The effect-size calculation was based on the Cohen's D measure of effect size (mean difference divided by overall standard deviation). We are enrolling a sufficient number of subjects in a 3-way cross-over design study so that we could both detect this effect AND be able to detect the pupil size effect with at least 80% power. In order to address the issue of powering for 2 outcome measures we will employ Bonferoni correction to be conservative and to achieve 80% power to detect BOTH the CAPS-5 and pupil size effects at the $\alpha=0.025$ level of significance (Bonferoni correction for 2 tests dictates that we divide the $\alpha=0.05$ level by 2). We calculated that with 36 subjects we could achieve greater than 80% power to detect effects with BOTH the CAPS-5 and pupil measure at the $\alpha=0.025$ level in a one-tailed test of significance (we are only interested in whether brexpiprazole is associated with lower CAPS-5 scores and pupil diameters than placebo and will only test this hypothesis and will not test whether placebo has a greater therapeutic effect than brexpiprazole). This calculation assumed an effect size of 0.3 for both the CAPS-5 score and for the pupil measure. It should be noted that the assumption of an effect size of 0.3 for the pupil measure is highly conservative. We can estimate the effect size for the between group differences in pupil size based on our pilot work where we compared pupil size in a group of patients with depression and anxiety ($n=5$) and healthy controls ($n=5$) using the pupillometric measure to be used in the proposed study. We hypothesize that the difference in locus coeruleus norepinephrine activity (which determines pupil size in this test) in PTSD subjects will be comparable to or larger than the differences in locus coeruleus activity in patients with depression associated anxiety. The basis for this hypothesis is that the patients we studied likely have less severe arousal-system dysfunction than PTSD patients who manifest symptoms of hypervigilance which is likely to activate locus coeruleus to a comparable or greater degree and be reflected in pupillometry. The effect size for the difference in resting pupil diameter in our anxious/depressed patients and healthy controls is 2.98 based on Cohen's D. However, it is appreciated that this is derived from a very small sample of subjects who are not the identical patient population that we will be studying so we assumed that it was most conservative to assume a lower effect size than 2.98. As a result, we assume an effect size of 0.3 which is likely quite conservative for power with respect to the pupil size measure. Thus, we propose to enroll 36 subjects in our study and believe that this is conservative for having more than 80% to detect effect sizes of 0.3 for both the CAPS-5 and pupil measures with an $\alpha=0.025$, which is adjusted from 0.05 for detecting effects on 2 primary outcomes at the 0.05 level, in one-tailed tests of significance.

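### The one-tailed rule in section 5.4 cannot confirm an increase in pupil diameter or separate it from no effect, although a possible increase is why the study is being done

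*Combined protocol and SAP*

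**What the plan says.** Section 4 (Background & Significance) gives the reason for the study as "preclinical data which suggest that there might be an increase in LC function with brexpiprazole at least with some doses". It sets the goal in neutral terms: "we propose to carry out a biomarker study to establish the effects of brexpiprazole on LC NE activity as a function of dose". It then presents pupillometry as the means of "addressing the uncertainty in dose generated by preclinical work indicating that, at least at some dosages, brexpiprazole may increase LC NE activity". The same section says that higher LC activity enlarges the pupil.

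Specific Aim 1 (section 3) has no direction: "Evaluate the effects of two doses of brexpiprazole on locus coeruleus (LC) norepinephrine (NE) neuron activity".

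The Purpose (section 2) and the Primary Hypothesis (section 5.3) do have one: "Brexpiprazole treatment will be associated with dose-dependent reduction in resting pupil diameter as a reflection of LC NE neuron target engagement".

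Section 5.4 follows the directional hypothesis. Each of the two outcomes, CAPS-5 and pupil diameter, is tested at 0.025 "in a one-tailed test of significance", and the section explains that "we are only interested in whether brexpiprazole is associated with lower CAPS-5 scores and pupil diameters than placebo and will only test this hypothesis". It adds that the investigators "will not test whether placebo has a greater therapeutic effect than brexpiprazole". Nowhere do the documents give a two-sided interval, or any rule for reading an increase in pupil diameter.

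**The concern.** A one-tailed test is easiest to defend when the opposite direction is implausible or of no interest. Here the protocol names the opposite direction as the source of the uncertainty it wants to resolve. If a dose lowers pupil diameter significantly, the plan answers the question for that dose. If a dose raises it, the formal result is only that a reduction was not shown, which is also the result for a dose with no effect.

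The two cases may lead to the same decision not to take that dose forward. They are still different points on the dose-response function that section 4 says the study will establish. With no prespecified way to tell them apart, any reading of an increase would be made after the data are seen, and against a written statement that only the reduction will be tested.

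**Working it through.** **Inputs from section 5.4:** 36 subjects in a three-way cross-over; effect size 0.3 as Cohen's d on the overall SD; one-tailed alpha 0.025 per outcome.

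**Assumptions (not in the documents):** within-subject correlation ρ from 0 to 0.9; no dropout; a paired comparison of one dose with placebo; a possible increase of the same size, 0.3 SD.

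**The plan's own figures.** The alpha split reproduces: 0.05 / 2 = 0.025. The stated power above 80% cannot be checked without ρ. On the paired comparison below, power per test is 42% at ρ = 0.5 and reaches 80% at ρ of about 0.805. The concern does not depend on this figure.

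**Set-up.** Standardised paired difference dz = 0.3 / √(2(1 − ρ)); noncentrality dz × √36 = 6 dz; 35 degrees of freedom; critical value t = 2.030. For example, at ρ = 0.5, dz = 0.3 / √1 = 0.300 and the noncentrality is 1.80.

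**If the dose truly increases pupil diameter by 0.3 SD:**

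| ρ | dz | P(planned lower-tail test rejects) | P(two-sided 95% CI wholly above 0) |
|---|---|---|---|
| 0 | 0.212 | 0.00069 | 0.235 |
| 0.5 | 0.300 | 0.00010 | 0.417 |
| 0.7 | 0.387 | 0.000012 | 0.618 |
| 0.805 | 0.480 | 9 × 10⁻⁷ | 0.800 |
| 0.9 | 0.671 | 2 × 10⁻⁹ | 0.975 |

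The planned test therefore fails to reject with probability at least 1 − 0.0007 = 0.9993. With no effect that probability is 1 − 0.025 = 0.975. Non-rejection is the expected result in both cases and does not separate them. The probability of declaring an increase is zero by construction, whatever its size.

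**Effect on the reduction test.** A two-sided 95% interval puts 0.025 in each tail, so the critical value for a reduction stays at 2.030 and its power does not change.

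**Error control.**
- One dose, counting a false CAPS-5 reduction, a false pupil reduction and a false pupil increase: 3 × 0.025 = 0.075, against 2 × 0.025 = 0.05 as planned.
- At least one false increase over the two doses: at most 2 × 0.025 = 0.05. A simulation of 400,000 null trials, with the doses sharing one placebo period and with equal variances and correlations, gives 0.0456.

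**Alternative that keeps 0.05 for one dose.** Splitting the pupil outcome's 0.025 into 0.0125 per tail raises the critical value to 2.342. At ρ = 0.805, power for a reduction falls from 0.80 to 0.70, and 44 subjects are needed to restore it (0.803).

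**The case against.** The best defence is that the test matches the stated hypothesis. The Purpose and the Primary Hypothesis both name a reduction, section 5.4 tests exactly that and gives its reason, and Aim 1 can be read as a general heading that they make specific. This stands: the one-tailed test is valid for its hypothesis. The conflict is with the rationale in section 4 and the neutral wording of Aim 1.

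Second, pupil diameter is measured at the start and end of every period, so an increase would be visible, and a one-tailed test does not forbid reporting a two-sided interval. This also stands, but no such interval is planned, and any reading of it would be post hoc. The clause on therapeutic effect fits CAPS-5 better than pupil diameter; for pupil diameter the exclusion rests on the statement that only the lower direction will be tested, which names pupil diameters explicitly.

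Third, the practical choice may be the same for an inactive dose and a harmful one. That limits the consequence but does not remove it, because the dose-response function is itself a stated aim.

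Fourth, the proposed interval is no cure-all. At ρ = 0.5 or below it would miss a true 0.3 SD increase more often than not, and without an equivalence margin it cannot establish no effect. The size of a possible increase is also borrowed from the reduction assumption. All of this is correct. The gain is a prespecified reading of an increase when the data support one.

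**Conclusion.** The concern holds, with high confidence, and should be fixed. As written, section 5.4 can confirm a reduction in pupil diameter but gives an increase of any size the same formal outcome as no effect. That follows from the lower-tail rule alone and needs no assumption about correlation.

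What could be gained does depend on assumptions. For a 0.3 SD increase with 36 completers, a two-sided 95% interval would identify it with probability 0.24 at ρ = 0, 0.42 at 0.5, 0.80 at 0.805 and 0.97 at 0.9. The primary reduction test remains valid. The defect is that the plan cannot formally address the possibility that motivated the study.

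**What to change.** In section 5.4:

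1. Remove the statement of sole interest in, and sole testing of, the lower direction for pupil diameter. Leave CAPS-5 as planned.
2. Prespecify two-sided 95% confidence intervals for pupil diameter, 2 mg minus placebo and 4 mg minus placebo.
3. State that an interval wholly above zero will be read as supportive evidence of increased LC activity at that dose, outside the Bonferroni family.
4. Keep the reduction test at one-sided 0.025 for each outcome.

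This needs no extra subjects and leaves the reduction test and its power as they are. The cost is in error control: the bound on any false conclusion rises from 0.05 to 0.075 for one dose, before counting two doses, and the chance of at least one false increase over the two doses is about 0.046. That is why the reading should be labelled supportive. If the sponsor prefers to hold 0.05 for one dose, 0.0125 per tail does so, but at ρ = 0.805 it lowers power for a reduction from 80% to 70% unless the sample rises to 44.

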6.4 SOP for Increased Suicidality

Any patient meeting clinical worsening criteria per interviews will be seen for a safety assessment by a study team psychiatrist experienced in working with patients with PTSD. If the patient is determined to be a significant suicide risk, one of the following three courses of action will be pursued:

A. Patients who contract for safety with the study physician and will be observed 24 hours/day by a responsible family member will be sent home and monitored by phone or added office visits as determined by the study physician.

B. Patients who are unwilling or unable to contract for safety will be accompanied by a staff member to the Duke Emergency Department.

C. Patients who are unwilling or unable to contract for safety and are unwilling to go to the Duke Emergency Department will be involuntarily committed via the Duke Medical Center protocol for Involuntary Commitment:

1. MD or appointed staff member remains with patient at all times
2. Staff member contacts [name] [name] or [name] [name] , Notary to begin process of IC forms
3. Staff member notifies Duke Public Safety., [name]
4. Staff member notifies Duke Emergency Department, [name]
5. Staff member collects patient demographics for police report custody order papers
6. MD does custody order papers
7. Petition notarized by [name] or [name]
8. Police officer escorts patient to Duke Emergency Department
9. MD to put report in CRMI database

The complete SOP for Increased Suicidality can be found in the Duke Sleep Center SOP book.

6.5 Safety Evaluations: Adverse effects will be assessed at every visit by study physician interview. Between visits, subjects will be called and a safety assessment will be carried out by the study coordinator during the call. The regular safety assessment calls will include assessment of suicidality, using the Columbia Suicide Severity Rating Scale items 4/5. If any adverse effects are identified, this will be discussed with a study physician and appropriate steps will be taken.

Benefits: Brexpiprazole has shown benefit in patients with schizophrenia and depression and it may also help PTSD symptoms. An improvement in PTSD symptoms, depression symptoms or in both may occur. The information learned from this study may benefit other patients with PTSD in the future.

6.6 Reproductive Risks: Although there is no human data available, caution should be advised in 3rd trimester pregnancies. Risk of neonatal extrapyramidal and withdrawal symptoms based on human data with other antipsychotics are known, there is currently no known risk of fetal harm based on animal data at up to 73x and 143x the maximum recommended human dose.

6.7 Costs to the Subject: There will be no charge to subjects for any of the tests, procedures, or professional services related to this study.

6.8 Subject Recruitment: Study participants will be recruited via bulletin/poster advertisements.

7. Privacy, Data Storage & Confidentiality:

1. Serious adverse events (SAEs) and other safety information will be collected and reported to the relevant government authority in accordance with the current Code of Federal Regulations
2. Safety Information is defined as, any information from any source containing information such as:
 - Adverse event or suspicion thereof
 - Lack of efficacy
 - Overdose/incorrect dosage (accidental or intentional)
 - Abuse/misuse (e.g., patients sharing medication) even without resulting adverse reaction

- Accidental exposure (e.g., child takes parent's medication)
- Medication error
- Withdrawal reactions
- Disease progression/exacerbation of existing disease
- Drug-drug/Drug-food interaction
- Reports of unexpected benefit
- Exposure to drug during pregnancy, where the embryo or fetus may have been exposed to medicinal products (either through maternal exposure or transmission of a medicinal product via semen following paternal exposure).
- Exposure to drug during lactation (including uneventful)
- Suspected counterfeit product
- Suspected transfer of infectious disease/agent by the medicinal product concerned.
- Product complaint report (any deficiencies related to the identity, quality, labeling, durability, reliability, efficacy, performance of a medicinal product, suspected counterfeit product)
- Pediatric use (if not an approved use)
- Occupational exposure
- Off-label use (if not part of the study design)

3. SAEs and safety information will be collected from first use of an Otsuka product until 28 days after discontinuation.

8. Privacy, Data Storage & Confidentiality: Study records identifying subjects will be kept confidential by law. Federal Privacy Regulations provide safeguards for privacy, security, and authorized access. Subjects will not be identified by name, social security number, address, telephone number, or any other direct personal identifier in study records disclosed outside of Duke University Health System (DUHS), except when required by law. For records disclosed outside of DUHS, subjects will be assigned a unique code number and key code kept in a locked file in [name] office. Study records may be reviewed to meet federal or state regulations. Reviewers may include representatives of the FDA and representatives of DUHS IRB. If subject records are reviewed by any of these groups, they may also need to review the entire medical record. Study results will be retained in research records and kept indefinitely.
